GS-US-454-4378:	Selonsertib 18 mg, GS-0976 20 mg, or GS-9674 30 mg for both monotherapy and combinations; Orally; Daily dosing
Reference Therapy in Drug Trial, Dose, Mode of Administration:	
	Placebo tablets; Orally; Daily
Criteria for Evaluation (HepQuant test parameters are the same for all studies):	
Baseline DSI:	DSI measured prior to randomization
ΔDSIi:	Change in DSI from baseline to time point, i
	Treatment Effect: ΔDSI i Treatment versus ΔDSI i Placebo
Primary Clinical Outcomes to link to baseline DSI and ΔDSIi:	
STELLAR 3:	Wk48: 1 Stage improvement in fibrosis without worsening NASH
	Wk48: Freedom from progression to cirrhosis
	Wk48: Freedom from decompensation, transplant, or death
	Wk240: 1 Stage improvement in fibrosis without worsening NASH
	Wk240: Freedom from progression to cirrhosis
	Wk240: Freedom from decompensation, transplant, or death
STELLAR 4:	Wk48: 1 Stage improvement in fibrosis without worsening NASH
	Wk48: Freedom from decompensation, transplant, or death
	Wk240: 1 Stage improvement in fibrosis without worsening of NASH
	Wk240: Freedom from decompensation, transplant, or death
GS-US-454-4378:	Endpoints as above for F3 and GJ F4 cases but only for 48 Weeks

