**Statistical Methods:**

We will determine the utility of the Disease Severity Index (DSI) from the HepQuant SHUNT test to monitor liver disease and treatment effects by measuring liver function and physiology. We propose a three-step analytical process to achieve this goal. First, without knowledge of treatment arm, we will track DSI and the change in DSI,  $\Delta$ DSI, from baseline to on-treatment and follow-up timepoints. Second, we will apply separate survival models to evaluate  $\Delta$ DSI as a continuous variable and a 2 point or more change in DSI as dichotomous variable in the prediction of changes in other tests or models of liver disease severity and clinical outcomes. In HCV, an increase in DSI of 2 or more has been associated with disease progression; and, a decrease in DSI of 2 or more has been associated with improvement after viral clearance. Third, once the treatment arms have been unblinded we will evaluate if the use of the HepQuant SHUNT test and DSI identify a treatment effect in the combined cohort of NASH F3 plus NASH F4; and we will compare DSI to the primary measures of efficacy in each of the clinical trials. In terms of DSI, a treatment effect will be defined from the difference between the  $\Delta$ DSI of the treatment arm versus the  $\Delta$ DSI of the placebo arm. The significance of this difference will be evaluated using a two-sided t-test. Furthermore, we will link treatment effect defined by DSI to effects of treatment on other tests and clinical outcomes (bleeding from varices or portal hypertensive gastropathy, ascites, encephalopathy, SBP, progression to cirrhosis, and patient mortality or liver transplantation). We will use both generalized estimating equations (GEE) and profile analysis – profile of DSI between treatment and placebo groups at each time point – for additional primary endpoint analyses.

We will also determine the ability of baseline DSI, performed prior to treatment, to assess the severity of liver disease by: 1. correlation with other baseline tests of liver disease severity; and, 2. prediction of risk for future clinical outcome.

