### 2.1 Primary Objective

The primary objective is to determine the utility of the Disease Severity Index (DSI) derived from the HepQuant SHUNT test, which measures liver function and physiology, for monitoring liver disease and treatment effects.

- Utility will be defined by measuring DSI and the change in DSI ( $\Delta$ DSI) across all treatment arms. DSI and  $\Delta$ DSI will be evaluated in real time.
- The clinical significance of changes in DSI will be evaluated by analyzing the relationship of  $\Delta$ DSI to changes in histologic stage of disease, standard laboratory tests, clinical models, or risk for clinical outcome. Some of the proposed comparative analyses will only be performed after unblinding of treatment arms and completion of analyses for the main Gilead trials and may be conducted by Gilead.
- Treatment effects will only be determined after unblinding the treatment arms and completion of the analyses for the main Gilead trials. In terms of DSI, treatment effects will be determined from the differences in DSI and  $\Delta$ DSI between treatment and placebo arms. The analyses will be conducted by Gilead.

**Clinically-meaningful outcomes.** As noted above, the subjects will be followed for clinical outcomes in the Gilead trials. In the case of STELLAR 3 and 4, the follow-up for clinical outcomes (bleeding from varices or portal hypertensive gastropathy, ascites, encephalopathy, liver-related death) will be up to 240 Wks – the  $\Delta$ DSI associated with development of clinical outcome at both Wk48 and Wk240 will be analyzed. In the case of GS-US-454-4378, the follow-up for clinical outcomes will be for 48 Weeks.

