### 5.3.2 Timing of HepQuant SHUNT testing

The basic design for HepQuant SHUNT testing is similar across the clinical trials:

[figure not shown]
- In all trials, the HepQuant SHUNT Test is initially performed at baseline, prior to any treatment, to assess liver function and physiology at entry to the trial, time  $t_0$ .

- The HepQuant SHUNT Test is then performed serially to monitor the change in function and physiology, relative to baseline, during the placebo/treatment and post-treatment follow-up periods of the study. In all cases, the study visits for the HepQuant tests will coincide and align with the protocol-defined visit windows for the GILEAD clinical trials.

In the STELLAR 3 and STELLAR 4 trials, the HepQuant SHUNT test will be administered at baseline and Weeks 24, 48, and 240. The total length of time subject will be in the SHUNT study is approximately 252 weeks. The study design for the STELLAR studies is shown in the figure below.

In the GS-US-454-4378 (NASH F3/4) trial, the HepQuant SHUNT test will be administered at baseline and Weeks 24 and 48. The total length of time subject will be in SHUNT study is 52 weeks. The study design for the GS-US-454-4378 (NASH F3/4) trial is shown in the following figure.

The specific comparative data collected in the HepQuant study are given in Appendix C. The results of the HepQuant SHUNT test will be transferred to Gilead who will analyze the test results in comparison to other procedures and clinical outcomes recorded in the Gilead trials. HepQuant will query Gilead for the results of these analyses.

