### 8.2.3 Statistical Considerations

Our Primary Objective is to determine the utility of the Disease Severity Index (DSI), derived from the HepQuant SHUNT test, to monitor liver disease and treatment effects. We propose a three-step analytical process to achieve this goal:

- First, without knowledge of treatment arm and for the group of subjects as a whole, we will track DSI and the change in DSI,  $\Delta$ DSI, from baseline to on-treatment and follow-up timepoints.
- Second, we will apply separate survival models to evaluate  $\Delta$ DSI as a continuous variable and a 2 point or more drop in DSI as dichotomous variable in the prediction of changes in other tests or models of liver disease severity and clinical outcomes.
- Third, after unblinding the study and completion of Gilead's analysis of the main clinical trial, we will make request of Gilead for allocation code to determine if there is a treatment effect, by comparing the difference between the  $\Delta$ DSI of the treatment arm versus the  $\Delta$ DSI of the placebo arm. The significance of this difference will be evaluated using two-sided t-tests and survival models.

Due to short enrollment period, only 5 STELLAR 3 and 4 STELLAR 4 subjects were enrolled into HQ-SHUNT-1701. STELLAR 3 and STELLAR 4 had two treatment arms (6 and 18 mg/d doses) and one placebo arm. Of the 9 subjects enrolled in HQ-SHUNT-1701, we would project that 6 would have been treated with selonsertib and 3 would have been taking placebo. Enrollment criteria, diagnosis, and F3/F4 stage of NASH is identical between the STELLAR studies and Gilead 454-4378. For the final analysis of treatment effects, once the code on all treatment arms from all studies is unblinded the projected 6 cases enrolled in HQ-SHUNT-1701 on selonsertib treatment from STELLAR studies will be added to the cases from Arm C of 454-4378 (selonsertib monotherapy) and the projected 3 cases enrolled in HQ-SHUNT-1701 on placebo from STELLAR studies will be added to the cases from Arm F (placebo) of the 454-4378 study.

Furthermore, we will link treatment effect defined by the change in DSI to effects of treatment on other tests and clinical outcomes (bleeding from varices or portal hypertensive gastropathy, ascites, encephalopathy, SBP, progression to cirrhosis, and

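### Step 2 of the primary analysis calls ΔDSI a predictor of outcomes without requiring it to be measured before them, and applies survival models to laboratory and MELD/Child-Pugh changes that have no defined event

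*Combined protocol and SAP*

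**What the plan says.** Section 8.2.3 sets out three steps for the primary objective. Step 2 fits separate survival models with ΔDSI, once as a continuous variable and once cut at 2 points, "in the prediction of changes in other tests or models of liver disease severity and clinical outcomes". The synopsis (Statistical Methods) says the same. Neither place names the visit at which ΔDSI is taken.

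The synopsis (Criteria for Evaluation) defines ΔDSI only as "Change in DSI from baseline to time point, i". Section 2.1 says that the ΔDSI "associated with development of clinical outcome at both Wk48 and Wk240 will be analyzed"; both weeks are themselves DSI visits.

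For GS-US-454-4378, section 5.3.2 states that "the HepQuant SHUNT test will be administered at baseline and Weeks 24 and 48", and section 2.1 states: "In the case of GS-US-454-4378, the follow-up for clinical outcomes will be for 48 Weeks". Section 8.2.3 reports that "only 5 STELLAR 3 and 4 STELLAR 4 subjects were enrolled into HQ-SHUNT-1701", and only those two trials have a Week 240 visit.

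By contrast, the secondary objective (sections 2.2 and 8.3.1) places baseline DSI before treatment, so the order of predictor and outcome is settled there.

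**The concern.** Prediction needs the predictor to be known before the outcome. Step 2 gives no landmark, no rule for a time-dependent covariate, no time origin and no censoring rule. An analyst could fit a Cox model of time to event up to Week 48 on Week 48 ΔDSI and still be following the text. For every subject with an event before Week 48, the covariate would then have been measured after the event. If decompensation worsens DSI, the model returns a hazard ratio above 1 even when DSI carries no forward information. If DSI does carry some, the estimate mixes the two.

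A separate problem is the kind of outcome. Changes in laboratory values and in MELD or Child-Pugh score are read at scheduled visits. The plan does not say what size of change counts as an event or when it is dated, so a survival model of those changes cannot be run as written.

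This matters because section 9.0 says the results may support the test as a tool, or even an endpoint, in later NASH trials. An association that partly reflects events changing DSI would be weak support for that.

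**Working it through.** **Order of measurement in GS-US-454-4378** (sections 2.1 and 5.3.2)

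| ΔDSI used | Outcomes that can follow it within follow-up |
|---|---|
| Week 24 | those after Week 24, up to Week 48 |
| Week 48 | none |

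The overall cap is 100 subjects and 9 came from the STELLAR trials, so this trial supplies at most 100 − 9 = 91.

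**Inputs from the documents.** SD of ΔDSI 3.5, with 3 and 4 in the table (section 8.1); 91 subjects as a ceiling, and the 60 named in section 8.1. The plan has no sample-size or power figure of its own for step 2; the section 8.1 table concerns a difference between arms.

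**Assumed inputs (not in the documents).** Event risk by Week 48 of 2, 5 or 10%; a DSI rise of 1 to 3 points after an event; half or one fifth of subjects with an event still tested at Week 48; no true prognostic value. The synopsis says "In HCV, an increase in DSI of 2 or more has been associated with disease progression". That reports an association with progression, not a rise caused by an event, so 2 points serves here only as a scale.

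**Size of the distortion.** Suppose ΔDSI is normal with the same SD in both groups and is shifted by the rise in subjects with an event. The log ratio of the two densities is then linear in ΔDSI with slope rise/SD². For rare events the hazard ratio per point is therefore about exp(rise/SD²).

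| SD | rise 1 | rise 2 | rise 3 |
|---|---|---|---|
| 3 | 1.12 | 1.25 | 1.40 |
| 3.5 | exp(1/12.25) = 1.09 | exp(2/12.25) = 1.18 | exp(3/12.25) = 1.28 |
| 4 | 1.06 | 1.13 | 1.21 |

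Cox fits to 400,000 simulated subjects per setting (SD 3.5, exponential event times, correlation of 0.5 between the Week 24 and Week 48 changes, also assumed) gave 1.17 to 1.18 for a rise of 2, nearly the same at each event risk and testing share. Week 24 ΔDSI in subjects event-free at Week 24, for later events only, gave 0.99 to 1.01.

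**Whether it would show.** As a yardstick only, since step 2 states no test, consider how often the 95% CI would exclude 1 with 91 subjects and a rise of 2. At 2% risk with one fifth tested after an event it does so in about 3% of simulated trials, so there is no visible effect. At 5% risk with half tested it does so in about 13%. The landmark stays at about 3 to 7%.

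**What the landmark leaves.** Expected events from Week 24 to Week 48 are n × [S(24) − S(48)], with S(48) = 1 − risk and, for exponential times, S(24) = √(1 − risk).

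| n | 2% | 5% | 10% |
|---|---|---|---|
| 91 | 0.9 | 2.2 | 4.4 |
| 60 | 0.6 | 1.5 | 2.9 |

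With 4 events, the 95% CI factor for the hazard ratio per point is about exp(1.96/(3.5 × √4)) = 1.32. An estimate of 1.2 would run from 1.2/1.32 = 0.91 to 1.2 × 1.32 = 1.59.

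**Progression to cirrhosis.** Section 8.2.2 lists this at Weeks 48 and 240 for F3 subjects, and no Week 24 histology is described. Nobody can be shown free of it at Week 24, so the landmark does not apply to it.

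**The case against.** The strongest reply is that the primary objective is monitoring. Sections 2.1 and 8.2.1 speak of relationships and association, and for that purpose a DSI taken at the same visit as the outcome is legitimate evidence. This stands. The fault lies in step 2 presenting such an analysis as prediction, not in doing it.

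The illustrated hazard ratio also restates an assumed rise. The documents give neither the rise nor the event risk; section 2.2 says only that outcomes accrue slowly. A subject who dies is not tested again, and a test after transplant measures a different liver, so full testing after events cannot be assumed. This stands too, and it is why no size can be claimed.

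A reader might infer that survival models are wrong throughout step 2. They are not: they suit decompensation, transplant and death, and discrete-time or interval-censored forms could handle visit-assessed progression if specified. A reader might also infer from the bar on earlier decompensation in section 5.2 that subjects with events are not retested. That is an entry criterion and does not settle the matter.

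Finally, the drug-trial sponsor runs the correlation analyses under a collaborative agreement (sections 1.1.3 and 5.3.3), which may already pair visits with outcomes. If so, the plan should say so. No success criterion hangs on step 2, and section 6.6.3 rules out management decisions based on the test, which limits the consequence.

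**Conclusion.** The point holds. Step 2 should fix the order of ΔDSI and outcome before it is called prediction, and laboratory and MELD/Child-Pugh changes need a different model or a defined event.

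The size is unknown and could be negligible. A hazard ratio of about 1.18 per point rests on an assumed 2-point rise after events, SD 3.5 and no true prognostic value; over SD 3 to 4 it is 1.25 to 1.13. The plan permits this analysis but does not require it, so a reader should not conclude that a reversed analysis is planned or that a large false signal is to be expected. The change is worth making because it is cheap and uses data already collected.

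**What to change.** State in section 8.2.3 and the synopsis, for each outcome, the ΔDSI visit and the model:

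1. **Decompensation, transplant, death:** Week 24 ΔDSI in subjects event-free and in follow-up at Week 24, for later events. A time-dependent covariate using only pre-event DSI amounts to the same in GS-US-454-4378, where no post-baseline DSI exists before Week 24. Report an exploratory hazard ratio with 95% CI, or a listing if events are very few.
2. **Week 48 histology (fibrosis improvement, and progression to cirrhosis in F3):** logistic regression, with Week 24 ΔDSI as the predictive analysis and Week 48 ΔDSI labelled as concurrent association.
3. **Laboratory and MELD/Child-Pugh change:** linear regression.
4. **Wording:** describe same-visit analyses as association, not prediction, and present Week 240 results, from at most 9 subjects, descriptively.

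The cost is SAP text and the agreement of the drug-trial sponsor; any pairing rule already in the collaborative agreement can be copied in. The downside is that events before Week 24 leave the landmark analysis and few remain, so the clinical-outcome result is exploratory.

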patient mortality or liver transplantation). In addition, we will use both generalized estimating equations (GEE) and profile analysis – profile of DSI between treatment and placebo groups at each time point – for additional primary endpoint analyses. The two NASH trials will be combined in the analysis of treatment effect.

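### The pooled treatment effect on ΔDSI is tested without adjusting for baseline DSI; an ANCOVA with a parent-programme term would be a modest, low-cost gain in precision

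*Combined protocol and SAP*

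**What the plan says.** The synopsis (Statistical Methods) defines the treatment effect as the difference in ΔDSI between the treatment and placebo arms and adds: "The significance of this difference will be evaluated using a two-sided t-test". Section 8.2.3 repeats the test and adds survival models: "The significance of this difference will be evaluated using two-sided t-tests and survival models". Both places name GEE and a profile analysis as further analyses of the primary endpoint. No covariate is named for any of these.

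The data are pooled: "The two NASH trials will be combined in the analysis of treatment effect". Section 8.2.3 explains how. Nine STELLAR subjects were enrolled, and "we would project that 6 would have been treated with selonsertib and 3 would have been taking placebo". The selonsertib subjects join Arm C of GS-US-454-4378 and the placebo subjects join Arm F. The sizes and ratio of Arms C and F are not stated.

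On what is measured, section 5.3.2 says: "In all trials, the HepQuant SHUNT Test is initially performed at baseline, prior to any treatment". On timing, the synopsis defines ΔDSI generally, as "Change in DSI from baseline to time point, i", and section 8.2.3 does not say which visit carries the treatment comparison. STELLAR subjects are tested at Weeks 24, 48 and 240. For the other trial, "In the GS-US-454-4378 (NASH F3/4) trial, the HepQuant SHUNT test will be administered at baseline and Weeks 24 and 48". Week 48 is therefore the last visit common to all trials.

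Named covariate control appears only in the Cox models for clinical outcome (synopsis and section 8.3.3).

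**The concern.** A t-test on change leaves in the error term whatever part of ΔDSI the baseline value predicts. That matters more in a small pool, where the arms can easily differ in baseline DSI by chance. The plan's own background suggests that change may depend on starting severity. In SOLAR-1 (sections 3.1.9 and 4.2.2) mean ΔDSI was -4.4 in transplant recipients without cirrhosis, -1.7 in those with cirrhosis and 0.2 in decompensated non-transplant subjects. Those were treated hepatitis C patients, so the figures motivate adjustment but cannot size it.

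Pooling adds a second issue. Randomisation protects the comparison within each trial. If the active-to-placebo ratio differs between STELLAR and GS-US-454-4378, a crude pooled difference also picks up any difference in mean ΔDSI between the two programmes.

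At stake are some precision and a safeguard for the pooled estimate, both available from data already collected.

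**Working it through.** **Inputs from the plan.** SD of ΔDSI 3.5 (section 8.1); difference of 2 (section 8.1 table and text); two-sided test (section 8.2.3); alpha 0.05 (section 8.1 table); projected STELLAR split 6:3 (section 8.2.3); cap of 100 subjects (synopsis).

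**Assumptions, not in the plan.** Arms C and F have 15 subjects each: (100 - 9)/6 ≈ 15, taking six arms A to F of equal size. The pool is then 15 + 6 = 21 against 15 + 3 = 18. The correlation rho between baseline and follow-up DSI is 0.5, 0.7 or 0.9. The SD of DSI is equal at both visits. There is no dropout and, for the power figures, no programme difference.

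**Step 1: the plan's own figure.** The table row with 29 per arm, difference 2, SD 3 and alpha 0.05 states power 0.80590. A noncentral-t calculation reproduces that figure only as a one-sided test; two-sided power is 0.704. At 30 per arm, SD 3.5 and a difference of 2, two-sided power is 0.586. This mismatch is a separate matter, but it means the contrast starts short of power.

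**Step 2: what baseline adjustment removes.** With equal SDs, the residual variance is Var(ΔDSI) × (1 + rho)/2. The residual SD is 3.5 × √((1 + rho)/2):
- rho 0.5: 3.03
- rho 0.7: 3.23
- rho 0.9: 3.41

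**Step 3: power for a difference of 2.** The t-test figures come from the noncentral t. The ANCOVA figures come from simulation (40,000 trials per cell, standard error at most 0.0025), which allows for chance imbalance in the covariate.

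| Pool | t-test | Baseline only, rho 0.5/0.7/0.9 | Baseline + programme, rho 0.5/0.7/0.9 |
|---|---|---|---|
| 21 v 18 | 0.410 | 0.504 / 0.457 / 0.419 | 0.495 / 0.449 / 0.412 |
| 16 v 13 | 0.315 | not tabulated | 0.38 / 0.34 / 0.31 |
| 11 v 8 | 0.213 | 0.254 / 0.229 / 0.211 | 0.246 / 0.223 / 0.206 |

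**Step 4: chance baseline imbalance is the same gain.** At 21 v 18 and rho 0.5:
- t-test variance: 3.5² × (1/21 + 1/18) = 1.264
- ANCOVA variance, ignoring the small cost of estimating the slope: 0.75 × 1.264 = 0.948
- variance due to baseline imbalance: (1 - 0.5)² × 3.5² × (1/21 + 1/18) = 0.316 (baseline SD is 3.5 at this rho)

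Since 0.948 + 0.316 = 1.264, the imbalance is already inside the t-test's standard error. Removing it is what produces the gain in Step 3.

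**Step 5: programme term.** The bias in the crude pooled difference, per 1-point programme difference in mean ΔDSI, is 6/(C + 6) - 3/(F + 3):
- C:F 15:15: 6/21 - 3/18 = 0.119
- C:F 10:20: 6/16 - 3/23 = 0.245
- C:F 20:10: 6/26 - 3/13 = 0

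At 15:15 the programme term raises the variance of the treatment estimate by about 2%.

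**The case against.** The strongest reply is that nothing here is wrong. An unadjusted two-sided t-test on change is valid in a randomised trial, and no conclusion becomes unsafe if the plan stays as it is. That stands. A reader might infer from the missing covariates that the planned test is invalid or biased; the documents do not support that.

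It can also be said that the gain rests on an unknown rho. That stands too. With equal SDs, the baseline SD is 3.5/√(2(1 - rho)), which is 3.5 at rho 0.5 and 7.8 at rho 0.9. The larger gain therefore needs a narrow spread of baseline DSI in a mixed F3/F4 pool, and the plan does not report that spread.

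On programme bias, section 8.2.3 says that eligibility, diagnosis and stage are the same across the pooled trials, and nothing in the documents points to a programme difference in ΔDSI. The bias is hypothetical, and a reader should not infer that the pooled estimate is biased. But matching eligibility does not settle the allocation ratio, so the safeguard keeps some value.

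Finally, the plan has other analyses. The survival models, GEE and profile analysis are real, and GEE or profile analysis may use baseline DSI as one of the repeated measures. The plan does not exclude adjustment, but it does not specify it, so the gap remains.

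**Conclusion.** The point holds as a recommendation for better precision. On the assumed pool of 21 against 18, power for a 2-point difference goes from 0.410 to 0.504, 0.457 or 0.419 with baseline DSI alone, and to 0.495, 0.449 or 0.412 with the programme term added, at rho 0.5, 0.7 or 0.9. The programme term removes a bias of 0.12 DSI points per 1-point programme difference if Arms C and F are equal in size, and none if they are 2:1. Arm sizes, rho, equal SDs and any programme difference are all assumptions.

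Three stronger readings should be resisted. ANCOVA does not rescue the power of this comparison: it stays below 0.51 at 21 against 18 throughout the range. Protection against chance baseline imbalance is not a second benefit on top of the power gain (Step 4). And the case does not extend to a fibrosis-stage term: no benefit of one has been shown, and with no stage effect it would cost a further 1 to 2 power points.

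**What to change.** In section 8.2.3 and the synopsis, make the main treatment comparison an ANCOVA of Week 48 ΔDSI on treatment, with baseline DSI as covariate and a parent-programme term (STELLAR against GS-US-454-4378). Keep the t-test, survival models, GEE and profile analysis as supportive. Section 2.1 has Gilead conducting the treatment-effect analyses, and section 8.2.3 has HepQuant requesting the allocation code. The model should therefore be written into the analysis request before that code is requested.

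The cost is SAP wording and two degrees of freedom. No new data are needed and no subject leaves the pool. The largest computed loss is about 1 power point, at rho 0.9 in the smaller pools (0.315 to 0.31 at 16 v 13; 0.213 to 0.206 at 11 v 8).
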